4.8.3 Follow-up Visit – Visit 5, (Week 5)

After treatment completion, subjects will continue with one more clinical study visit to measure the long-term pro-cognitive effect of TLT. The follow-up visit will typically occur at the MGH Center for Anxiety and Traumatic Stress Disorders (CATSD) in Boston but could be performed at the Martinos Center for Biomedical Imaging in Charlestown if preferable to the subject.

At Visit 5, the following will be performed:

- Concomitant medications form
- ADVERSE EVENTS FORM
- ASQ (self-rated)
- SDQ (self-rated)
- NEURO-QoL (self-rated)
- SFI (self-rated)
- SAFTEE (self-rated)
- PANAS (self-rated)
- Cognitive tests

4.8.4 Termination

We will encourage subjects to complete the follow-up visit in the study regardless of discontinuation of the TLT sessions.

4.9 Scales & Forms

We will offer clinical interviews and study forms in English. All scales will explore the past 7 days except for SCID (lifetime), PANAS (past 5 min), TSRQ and PBQ (both past session). Below are brief descriptions of the forms that will be utilized in this study.

- **Structured Clinical Interview for DSM-IV (SCID-I/P)** – The SCID-I/P, administered by the clinician, proceeds by modules to diagnose the different psychiatric disorders. Questions here are asked exactly as written, and each is based on the individual criteria from DSM-IV. Answers are generally rated on a scale of 1-3 (1 = doubtful, 2 = probable, 3 = definite), and based on the number of positive answers, a diagnosis is determined. The entire SCID-I/P is administered at screening as per Table 1.
- **Symptoms of Depression Questionnaire (SDQ)** – This is a comprehensive measure of depression that includes the assessment of symptoms in the anxiety–depression spectrum. It assesses irritability, anger attacks, and anxiety symptoms together with the commonly considered symptoms of depression. Analysis of the factor structure of the SDQ identified 5 subscales, including one in the anxiety–depression spectrum, with adequate internal consistency and concurrent validity.
- **Anxiety Symptoms Questionnaire (ASQ)** – This is a 17-item self-report questionnaire measuring the frequency and intensity of 17 symptoms of anxiety, including nervousness, worrying, irritability, trouble relaxing, insomnia, lack of energy, difficulty concentrating, somatic symptoms, and impairment in functioning due to anxiety.
- **Systematic Assessment for Treatment Emergent Events (SAFTEE-SI)** – The SAFTEE is a commonly used instrument originally developed by NIMH and adapted into a self-report instrument. The version of the scale that we plan to use

is the same used by the multi-center, NIMH-sponsored CO-MED trial, and it examines in a systematic fashion all possible treatment-emergent side effects and probes specific adverse symptoms, including suicidal thoughts and behaviors, and self-injurious behavior.

- **Positive and Negative Symptoms Questionnaire (PANAS)** – The 20-item PANAS, comprises two mood scales, one measuring positive affect and the other measuring negative affect. Each item is rated on a 5-point scale ranging from 1 = very slightly or not at all to 5 = extremely to indicate the extent to which the respondent has felt this way in the indicated time frame. The authors have used the scale to measure affect at this moment, today, the past few days, the past week, the past few weeks, the past year, and generally (on average).
- **Adverse Events Form**- the Adverse Events Form captures any adverse event (serious or otherwise) specifically related to the application of the TLT. This form will help to determine if the side effects of the TLT are too great for a participant to continue in the study.
- **Quality of Life in Neurological Disorders (Neuro-QoL Item Bank v2.0 – cognition function– short form)** - The cognitive section of the Neuro-QoL is an 8 item self-rated measure of both executive function and general concerns. It measures perceived difficulties in cognitive abilities (e.g., memory, attention, and decision making) or in the application of such abilities to everyday tasks (e.g., planning, organizing, calculating, remembering and learning).
- **Massachusetts General Hospital Sexual Functioning Inventory (MGH-SFI)** - This is a subject-rated self-report outcome measure that quantifies sexual dysfunction into 5 functional domains (“interest in sex,” “sexual arousal,” “ability to achieve orgasm,” “ability to maintain erection” [males only], and “sexual satisfaction”).
- **The TLT Self-Report Questionnaire (TSRQ)** – An open-ended questionnaire focusing on potential inconveniences and discomforts from the TLT.
- **Concomitant medications form** – This form will be completed at every TLT study visit, including the screening visit, as a safety-monitoring tool.
- **The Perceptions of Blinding Questionnaire (PBQ):** the PBQ is a self-report questionnaire to determine the degree to which the participant believes s/he is receiving the treatment or the sham.

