4.2 Study Design

This study is a single-blind, sham-controlled, study on the use of Transcranial continuous light therapy (c-TLT) and pulse light therapy (p-TLT) as an enhancer of cerebral blood flow in healthy subjects.

We expect that out of 30 subjects enrolled 10 subjects will be eligible to complete a sequence of three sessions of Transcranial Light Treatment (TLT) and sham.

All eligible subjects will receive two TLT sessions and one of sham (s-TLT) within the course of 5 weeks. While the sequence (c-TLT, s-TLT, p-TLT) will be the same for all subjects, the subjects will be blind to the specific mode of function used in each session.

The study site (MGH) will have one Litecure device, which will recognize the subjects' codes generated by the study statistician. Only subjects will be blind to the treatment group assignment. The Sham treatment consists of applying all the procedures for the delivery of the TLT, while actually delivering no light. The blinding of the sham will be effective because the radiation is not visible and because the active therapy (continuous or pulsed) will not produce any subject-discriminable difference from sham, e.g., skin warming. The sham treatment will mimic the TLT procedure. The treatment will be bilateral and applied to the frontal areas with two application sites on the left side and two on the right side [left and right forehead centered on EEG sites on F3, F4, Fp1, Fp2]. Energy is administered with a radiation wavelength of 830 nm. The duration of irradiation is 20 minutes at each application site (the 4 sites are irradiated at the same time which is equivalent to 20 minutes of total time). The entire sessions is estimated to last about 1.5 hours. The additional time is needed to have the subject complete a urine toxicology and self-report forms, to prepare the subject, to place the necessary protections (e.g. goggles), to inspect the subject's skin, to complete DCS before and after TLT, to set the TLT devices, and to give the subject time to rest after the irradiation. TLT treatment will only be administered by licensed physicians (i.e. MDs) who are on study staff. All staff who deliver treatment must pass training that is approved by the MGH Laser Safety Committee. The treatment will follow these specifications: wavelength 830 nm; average irradiance 54.8 mW/cm²; average fluence of 65.8 J/cm² (consistently with energy density used in the ELATED-2 study at MGH with the device Omnilux New U).

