The trained staff administering the TLT will use utmost care to never shine the light in or near the eyes of the subject safety goggles will be selected based on the TLT biophysical properties, in accordance to the Occupational Safety and Health Administration (OSHA) guidelines. The delivery of the TLT is expected to last 20 min total (simultaneous application on the left and right forehead). The subject will be asked to rest for five minutes after the delivery of TLT. The skin at the sites of the application will be inspected again prior to dismissing the subject. A log with the dates of treatment delivery per each study subject will be kept at MGH CATSD (Boston).

During TLT-DCS Visit 2-4, subjects will receive TLT-c (Visit 2), TLT-s (Visit 3) and TLT-p (Visit 4).

The following tasks will be completed prior to every TLT session:

- Utox
- Concomitant medications form
- ADVERSE EVENTS FORM
- ASQ (self-rated)
- SDQ (self-rated)
- NEURO-QoL (self-rated)
- SFI (self-rated)
- SAFTEE (self-rated)
- PANAS (self-rated)
- EEG- Recording
- DCS – Spectroscopy

The following tasks will be completed after every TLT session:

- DCS – Spectroscopy
- EEG- Recording
- Cognitive tests
- PANAS (self-rated)
- TSRQ (self-rated)
- PBQ (self-rated)

Subjects shall be instructed to contact the investigator or a member of his staff at any time between visits concerning adverse events or worsening of symptoms.

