4.17 Clinical Adverse Events

4.17.1 Overview and Definitions

All adverse events will be recorded from the time of Informed Consent through study completion, or termination. The Adverse Event CRF must be completed and submitted to the IRB, FDA, and Litecure, as required. Regulations for adverse event handling and reporting contained in the FDA and ICH Guidelines will be adhered to.

Consideration of Adverse Events will hereafter consist of Adverse Events, Serious Adverse Events, and Adverse Device Effects, including Anticipated Adverse Device Effects and Unanticipated Adverse Device Effects.

- Adverse Event is defined as any untoward/undesirable clinical occurrence in a clinical investigation of a subject using a device and/or product and which

does not necessarily have a causal relationship with this treatment. An Adverse Event can therefore be any unfavorable and/or unintended sign, symptom, or disease temporally associated with the use of a device product, whether or not considered related to the device product. Only abnormal laboratory values that are deemed clinically significant by the investigator will be classified as adverse events.

- Serious Adverse Event is defined as any untoward/undesirable adverse experience that results in any of the following outcomes: 1) death; 2) a life-threatening adverse experience; 3) inpatient hospitalization or prolongation of existing hospitalization; 4) a permanent/persistent or significant disability/incapacity or a congenital anomaly/birth defect; 5) important medical events that may not result in death, be life-threatening, or require hospitalization may be considered a serious adverse experience when, based upon appropriate medical judgment, they may jeopardize the subject and may require medical or surgical intervention to prevent one of the outcomes listed in this definition.
- Anticipated Adverse Device Effect is defined as any adverse effect related to the device or procedure, which is identified in the protocol.

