4.17.3 Reporting Procedures for All Adverse Events

After review with the subject by the study site personnel, all Adverse Events occurring during the study, whether or not attributed to the TPBM-1000 device or TLT procedure, observed by the Investigator or reported by the subject, will be documented in the subject's source document and on the appropriate CRF pages. The following attributes must be assigned:

1. Description of event
2. Date of onset
3. Date of resolution (if applicable)
4. Seriousness
5. Relationship to the study device and/or procedure(s)
6. Intensity
7. Action(s) taken

8. Outcome(s)

Intensity is defined as a measure of the severity of a reaction, effect or experience. The measurement(s) are described as mild, moderate or severe. The event itself, however, may be of relative minor medical significance.

The intensity of Adverse Events is assessed as mild, moderate or severe according to the following index scale:

Mild

The Adverse Event is transient, requires no treatment, and does not interfere with the subject's daily activity.

Moderate

The Adverse Event introduces a low level of inconvenience or concern to the subject and may interfere with daily activities, but is usually ameliorated by simple therapeutic measures.

Severe

The Adverse Event interrupts the subject's usual daily activity and requires systematic therapy or other treatment.

If the Adverse Event is of such intensity in the Investigator's judgment that it warrants withdrawal from the study, the subject should be withdrawn from treatment. The subject should be given appropriate care under medical supervision until symptoms resolve.

The relationship of an Adverse Event to the study device or procedure will be graded as follows:

None

The Adverse Event is not associated with the study device use.

Remote

The temporal association is such that the study device is not likely to have had an association with the observed Adverse Event.

Possible

This causal relationship is assigned when the Adverse Event:

- a) Follows a reasonable temporal sequence from device use, but
- b) Could have been produced by the subject's clinical state or other modes of therapy administered to the subject.

Probable

This causal relationship is assigned when the Adverse Event:

- a) Follows a reasonable temporal sequence from device use;
- b) Abates upon discontinuation of the treatment;
- c) Cannot be reasonably explained by known characteristics of the subject's clinical state.

Definite

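### Section 4.9 limits the Adverse Events Form to TLT-related events, while 4.17.1 and 4.17.3 require every adverse event to be recorded whatever its cause

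*Combined protocol and SAP*

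**What the plan says.** Section 4.9 (Scales & Forms) describes the form in two sentences. The first sets its scope: "the Adverse Events Form captures any adverse event (serious or otherwise) specifically related to the application of the TLT". The second gives its use: "This form will help to determine if the side effects of the TLT are too great for a participant to continue in the study".

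Section 4.17 sets a wider rule. Under 4.17.1, "All adverse events will be recorded from the time of Informed Consent through study completion, or termination", and an adverse event is an occurrence that "does not necessarily have a causal relationship with this treatment". Section 4.17.3 requires documentation of "all Adverse Events occurring during the study, whether or not attributed to the TPBM-1000 device or TLT procedure", in the source document and on CRF pages. Relationship is one of eight attributes assigned to each event. It has five grades: None, Remote, Possible, Probable and Definite. None is defined as "The Adverse Event is not associated with the study device use".

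The Adverse Events Form appears in the 4.8.2 list headed "The following tasks will be completed prior to every TLT session", in the Visit 5 list (4.8.3) and in the exit-visit list (4.19.1). The schedule of procedures marks an adverse-event assessment at all five visits.

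On blinding, 4.2 states "Only subjects will be blind to the treatment group assignment" and fixes the order as c-TLT, sham, p-TLT for everyone. Section 3.2 on the LED system describes the operator as blinded too.

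**The concern.** A form that admits only related events and a rule that demands all events cannot both be followed. In 4.17.3, relationship is a property of an event already recorded. In 4.9, it is the test for recording the event at all.

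Three uses of the data depend on complete capture:

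- the safety endpoint in the Study Summary, which takes reported events in the week after each session;
- the section 5.6 tabulation of events by type;
- the investigator's monthly review of adverse event reports under 4.17.2, which can lead to pausing enrolment, changing the protocol or ending the study.

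An event left off the form because someone thought it unrelated could not be regraded later, and a pattern of unexpected events would be harder to see. The judgement may also not be neutral between sessions, because anyone who knows the order knows which week followed sham.

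**Working it through.** No sample size, rate or test statistic is involved, so the check is a comparison of the texts.

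**1. Scope.** Section 4.9 does not contain the word *only*. Its second sentence speaks of side effects of the TLT, which supports the narrow reading. Section 4.17.3 says the reverse in terms.

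**2. The relationship scale.** An event graded None cannot meet the 4.9 description, and one graded Remote hardly can. So up to two of the five grades in 4.17.3 would be empty, or nearly so, on a form completed to 4.9.

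**3. The schedule.** The table sets out what each scheduled form covers.

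| Form completed | Period covered | Admitted under 4.9 | Required under 4.17 |
|---|---|---|---|
| Week 1, screening | from consent | nothing; no TLT yet | all events |
| Week 2, before c-TLT | screening to first session | nothing; no TLT yet | all events |
| Week 3, before sham | after c-TLT | events judged related | all events |
| Week 4, before p-TLT | after sham | unclear; depends on whether TLT includes sham | all events |
| Week 5, follow-up | after p-TLT | events judged related | all events |

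Two of the five scheduled forms therefore precede any TLT and, on a literal reading of 4.9, could hold no event. That contradicts the instruction to record from consent. Of the remaining 5 − 2 = 3, one covers the week after sham.

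**4. Events not caused by the light.** Section 4.17.2 foresees a mild allergic response to EEG gel, and 4.20.1 an allergic reaction to eye-pad adhesive. It is unclear whether a form tied to the application of TLT would take the first of these.

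**5. Who applies the filter.** The protocol does not say who completes the form. It is not marked as self-rated, whereas the questionnaires listed beside it are, and 4.17.3 describes review with the subject by site personnel. Completion by staff is therefore a reasonable inference, not a stated fact. If staff complete it, the fixed order in 4.2 tells them the mode from the visit number. The statement in 3.2 that the operator is blinded conflicts with 4.2, and is hard to sustain when every subject has the same order.

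**6. What reaches the analysis.** Section 4.17.1 refers to an Adverse Event CRF and 4.17.3 to CRF pages. Neither says whether this is the Adverse Events Form. Section 5.6 does not name its data source.

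**The case against.** The best defence is that 4.17.3 is the operative rule and 4.9 only a short description of a form with a narrower purpose, namely judging tolerability. On that view the Adverse Event CRF is a separate document and nothing is lost. This may be what was intended, but the protocol does not say so, and no visit list names a second adverse-event form.

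There is also parallel capture. SAFTEE is self-rated by blinded subjects before each session and at Visit 5, looks back seven days, and involves no staff attribution. The open-ended TSRQ follows every session, sham included. These reduce the chance that an event goes entirely unseen. However, the protocol does not say that either instrument feeds the 5.6 counts.

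A reader might infer something stronger: that events after sham are excluded by definition, so that the sham rate is driven to zero and the comparison with active light is biased. The documents do not support this.

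- Usage of TLT is mixed. Section 4.2 contrasts TLT sessions with sham, but the Study Summary endpoints, 4.8.2 and the schedule all label sham as a form of TLT.
- Sham involves the full application procedure without light, and 4.17.3 grades relationship to device or procedure. An event after sham can therefore count as related.
- Section 5.6 tabulates by event type, not by mode, and 5.7 is descriptive. No active-versus-sham contrast of adverse events is planned that could be distorted.

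**Conclusion.** The contradiction between 4.9 and 4.17.1/4.17.3 is explicit and should be corrected. If 4.9 is followed, events judged unrelated can drop out of the one-week safety endpoint and the 5.6 counts. These could include some sham-week events and any that occur before the first session.

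The size of the loss cannot be given. It depends on how staff read the definition, on whether a separate CRF exists, and on whether SAFTEE or TSRQ entries are carried into the adverse-event data. The point that the filter may differ by session rests on two inferences: that staff complete the form, and that the fixed order reveals the mode despite the statement in 3.2. A claim of a zero sham rate or of a biased comparison with sham would go beyond the text. The primary cerebral blood flow analysis in 5.5 is not affected.

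**What to change.** Reword the 4.9 entry so that the form captures *any adverse event since the last visit (from consent, for the first form), whether or not considered related to TLT, including after sham sessions*. Record relationship on the form as the five-grade field already defined in 4.17.3.

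State in 4.9 or 4.17.1 that this form is the Adverse Event CRF and that it supplies the 5.6 counts. If a separate CRF is intended, name it, add it to the visit lists, and say which document feeds 5.6.

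Reconcile the operator-blinding statement in 3.2 with 4.2, so that it is clear what the person recording events knows about the session mode.

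The cost is one reworded sentence, a form header, a line on the data source, and a few more entries per visit. The schedule of visits and assessments does not change.

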Study Population: Subjects eligible for study participation will be healthy by Structured Clinical Interview for Diagnostic Statistical Manual-IV (SCID) criteria. Subjects will be between 18-70 years of age (have not had 71st birthday) on the date of screening. Subjects who will be permitted into the study include those who meet all the inclusion criteria and have none of the exclusion criteria.

Duration of Participation:	Subjects will be followed in the study for 5 weeks.
Endpoints:	
Engagement of cerebral blood flow – The effect of TLT on cognition will be assessed before and after each session (c-TLT, s-TLT and p-TLT) by measuring the Diffuse Correlation Spectroscopy (DCS) signal.
 
Engagement of cerebral electrical activity – The effect of TLT on brain electrical waves will be assessed before and after each session (c-TLT, s-TLT and p-TLT) by measuring the Electro-Encephalographic (EEG) signal.
 
Engagement of cognitive circuitry – The effect of TLT on working memory will be assessed immediately after each session by n-back task.
 
Safety - The safety endpoints will evaluate any reported adverse events within one week from each sessions of TLT.

Entry Criteria: Inclusion Criteria	
	
 1. Subject's age at screening will be between 18 and 70 years old (inclusive). 2. Women of child-bearing potential must use a double-barrier method for birth control (e.g. condoms plus spermicide) if sexually active. 3. Subject Informed Consent obtained in writing in compliance with local regulations prior to enrollment into this study. 4. The subject is willing to participate in this study for at least 5 weeks.
Exclusion Criteria:	
	
 1. The subject is pregnant or lactating. 2. The subject is on any psychotropic medication. 3. Psychotherapy is exclusionary unless the subject has had at least 8 weeks of treatment prior to the screening visit. 4. Any current psychiatric disorder (per SCID assessment) 5. Substance or alcohol dependence or abuse in the past 6 months. 6. History of a psychotic disorder or psychotic episode (current psychotic episode per SCID assessment). 7. Bipolar affective disorder (per SCID assessment). 8. Unstable medical or neurological illness, defined as any illness which is not well-controlled with standard-of-care medications (e.g., insulin for diabetes mellitus, HCTZ for hypertension). 9. Suicidal or homicidal ideation as determined by SCID screening.

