4.1 Rationale

The specific aims of this study are:

1. To assess the change in cerebral blood flow induced by the Transcranial Continuous and Pulse Near-Infrared Light Therapy (c-TLT and p-TLT) in healthy subjects
2. To correlate with cognitive performance the change in cerebral blood flow induced by the Transcranial Continuous and Pulse Near-Infrared Light Therapy in healthy subjects
3. To correlate with brain electrical activity the change in cerebral blood flow induced by the Transcranial Continuous and Pulse Near-Infrared Light Therapy in healthy subjects
4. To correlate with skin pigmentation the change in cerebral blood flow induced by the Transcranial Continuous and Pulse Near-Infrared Light Therapy in healthy subjects
5. To assess the safety and tolerability of the Transcranial Continuous and Pulse Near-Infrared Light Therapy in healthy subjects

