5.6 Safety Analyses

The number and percent of Adverse Events through study completion will be presented by adverse event type.

5.7 *Additional Safety Analyses*

Descriptive statistics for safety endpoints will include number of subjects, mean, standard deviation, median minimum and maximum for continuous variables, and frequencies and percentages for categorical variables.

6 Ethical Review & Regulatory Considerations

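### Aim 5 covers tolerability, but no planned summary shows adverse events by light mode and sham or uses the discomfort reports (TSRQ) that blinded subjects give after each session

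*Combined protocol and SAP*

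**What the plan says.** Section 4.1 gives the fifth aim as "To assess the safety and tolerability of the Transcranial Continuous and Pulse Near-Infrared Light Therapy in healthy subjects". The Endpoints entry of the Study Summary narrows this to adverse events: "The safety endpoints will evaluate any reported adverse events within one week from each sessions of TLT". Tolerability has no definition of its own.

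Section 5.6 plans one table: "The number and percent of Adverse Events through study completion will be presented by adverse event type". Section 5.7 adds generic descriptive statistics for safety endpoints and names no instrument. Neither section mentions treatment mode. The only planned comparisons between modes are the paired t-tests on change in cerebral blood flow in section 5.5.

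The TSRQ is described in section 4.9 as "An open-ended questionnaire focusing on potential inconveniences and discomforts from the TLT", and its reference period is the session just finished ("TSRQ and PBQ (both past session"). Section 4.8.2 lists it among the forms under "The following tasks will be completed after every TLT session", and the schedule table in section 8 marks it after the sessions in Weeks 2, 3 and 4. The order is the same for everyone: "subjects will receive TLT-c (Visit 2), TLT-s (Visit 3) and TLT-p (Visit 4". Section 4.2 states that "the subjects will be blind to the specific mode of function used in each session".

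**The concern.** The aim asks about c-TLT and p-TLT separately, and the trial collects what is needed for a first answer. Each subject reports on discomfort straight after continuous light, after sham and after pulsed light, without knowing which was given. Section 5 makes no use of these reports. The adverse event table it does plan is not stated to separate light from sham.

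Sham matters here because the cap, the DCS probes and the EEG headset are used in all three sessions, and section 4.17.2 itself expects mild discomfort from the headset. A count by event type over the whole study cannot show whether a complaint followed light or sham. The report could then describe the procedure as well or poorly tolerated without showing that the light had any part in it.

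**Working it through.** The plan states no figure for tolerability, so there is nothing to reproduce. The check sets the sections side by side and then asks what ten subjects can show.

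**1. From subject report to planned result**

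- Section 4.17.1 defines an adverse event broadly, whether or not it is related to the device. Section 4.17.3 requires events reported by the subject to be documented. Section 4.20.1 lists application-site discomfort, pain and warmth, and headache, as adverse events seen with TLT. Discomfort written on the TSRQ therefore qualifies as an adverse event.
- No section says that TSRQ text is reviewed for adverse events or transferred to that record.
- The Adverse Events Form is scheduled before each session and at Visit 5 (sections 4.8.2, 4.8.3 and 8), not straight after exposure. Section 4.9 describes it as limited to events related to TLT, which is narrower than section 4.17.3. Section 4.2 says that only subjects are blind, so this judgement of relatedness may be made by staff who know the mode.
- An event that does reach the record enters the section 5.6 table, which has no stated split by mode.

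**2. What a table by type alone cannot show (illustrative counts)**

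Suppose 4 of 10 subjects have a headache after exactly one session each.

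| | Section 5.6 table | p-TLT | Sham | p-TLT only / sham only |
|---|---|---|---|---|
| All after p-TLT | 4 of 10 | 4 of 10 | 0 of 10 | 4 / 0 |
| All after sham | 4 of 10 | 0 of 10 | 4 of 10 | 0 / 4 |

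The planned table is identical in both cases. The table by mode is reversed.

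**3. Amount of data**

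Section 4.5 expects 10 subjects with analysable data. With complete data this gives 10 × 3 = 30 TSRQ forms: 10 × 2 = 20 after light and 10 after sham. Section 4.5 needs only one session for a subject to count, so 30 is a maximum.

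**4. Precision per mode**

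The exact (Clopper-Pearson) 95% limits for x of n subjects are the 2.5% quantile of Beta(x, n − x + 1) and the 97.5% quantile of Beta(x + 1, n − x). For x = 0 the upper limit is 1 − 0.025^(1/10) = 30.8%.

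| Subjects with discomfort | Exact 95% interval |
|---|---|
| 0 of 10 | 0% to 30.8% |
| 1 of 10 | 0.3% to 44.5% |
| 3 of 10 | 6.7% to 65.2% |
| 4 of 10 | 12.2% to 73.8% |

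The chance of at least one report in ten subjects is 1 − 0.9^10 = 65% at a true rate of 10%, and 1 − 0.8^10 = 89% at 20%.

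**5. Whether a test against sham would help**

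This assumes a two-sided exact McNemar test at 5%; the plan sets no level. With all discordant subjects in one direction, five give p = 2 × 0.5^5 = 0.0625 and six give p = 2 × 0.5^6 = 0.031. At least six of the ten must therefore be discordant. Power is the multinomial probability of outcomes with p ≤ 0.05. If 5% of subjects have discomfort on sham only, power is 12% when 40% have it on light only, and 46% when 60% do. These rates are assumptions.

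**The case against.** The strongest reply is that the adverse event rules already cover this. Subject-reported discomfort qualifies as an adverse event, and failing to record it would be a departure from the protocol rather than a gap in it. The self-rated SAFTEE looks back seven days, so at Visits 3, 4 and 5 it covers the weeks after c-TLT, sham and p-TLT. Section 5.7 is worded for continuous and categorical safety endpoints and could be stretched to include the TSRQ.

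Much of this stands, and it rules out a stronger reading. A reader might infer that discomfort written on the TSRQ is lost from every result, or that tolerability rests only on what unblinded staff choose to record. The documents do not support either: sections 4.17.1 and 4.17.3 require such reports to be documented, and the SAFTEE is a second self-report by blinded subjects. What remains is that no transfer step is stated, the SAFTEE has no named analysis either, the Study Summary ties safety endpoints to adverse events, and no safety result is planned by mode.

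A second objection also stands. A reader might infer that a paired comparison with sham would isolate the effect of light, since the procedures are otherwise the same. It would not. Every subject has c-TLT first, sham second and p-TLT third, so mode cannot be separated from novelty, habituation or any other effect of visit. With the power shown above, a non-significant test could also be misread as evidence of good tolerability. Finally, the form itself is not in the documents, so whether it has any closed item cannot be checked.

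**Conclusion.** The point holds as a gap in the analysis plan. As written, the plan cannot answer the tolerability part of aim 5 for either light mode: adverse events are not stated to be split by mode, and up to 30 TSRQ forms have no planned summary. That comparison with sham is unplanned; nothing prevents it from being made.

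The gain from closing the gap is modest. With 10 subjects the result is a descriptive table with wide intervals, and the fixed order limits what it can attribute to light. It concerns the fifth aim and leaves the primary analysis untouched. The change is still worth making because the data are already being collected and the cost is small. The conclusion rests on reading section 5.6 as pooled over modes, since it states no split, and on the TSRQ being open-ended as section 4.9 describes it.

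**What to change.** 1. In section 1 and section 5, name discomfort reported on the TSRQ as the tolerability outcome for aim 5.
2. Add one yes/no item to the TSRQ, before the open text: any discomfort during this session.
3. Have the text coded to the terms in section 4.20.1 by someone masked to mode. The order is fixed, so the coder must not see visit number or date either. Show warmth on its own line and read it beside the blinding questionnaire (PBQ), because warmth may reveal the mode.
4. In sections 5.6 and 5.7, tabulate TSRQ discomfort and adverse events by c-TLT, sham and p-TLT. Assign each adverse event to the preceding session, and list events before the first session separately. Give the number of subjects with exact 95% intervals, and for each light mode the numbers with discomfort on light only and on sham only.
5. Label the table descriptive, include no McNemar test, and state that mode is confounded with visit order.

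The cost is one REDCap item on an existing form, coding of at most 30 short texts, and one table. Visits, sessions and sample size do not change. The drawbacks are the wide intervals and the order caveat.
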